## 1.0 PROTOCOL SYNOPSIS

### STUDY TITLE

A Prospective, Randomized Study to Evaluate the Safety and Effectiveness of Steerable Ureteroscopic Renal Evacuation (SURE) using the CVAC® Aspiration System Compared to Baskets for the Removal of Renal Calculi Following Ureteroscopic Laser Lithotripsy

### SAMPLE SIZE

Sample size is based on the stone free rate (SFR) where stone free status is defined as zero residual fragments at 30 days observed on non-contrast CT (NCCT) by blinded central reviewer(s). Sample size determination was performed assuming the  $SFR_{CVAC} = SFR_B = 25\%$ . A sample size of  $N=116$  (58 per group using 1:1 randomization) produces at least 80% power to reject the non-inferiority null hypothesis assuming a one-sided  $\alpha=0.05$  normal approximation test.

### PRIMARY ENDPOINT

The primary efficacy endpoint is the SFR, where stone free status is defined as zero residual fragments at 30 days observed on non-contrast CT (NCCT) by blinded central reviewer(s). The SFR is calculated by determining the number of subjects in each treatment arm with a stone free status of 'yes' and dividing that by the total number of subjects treated in the respective treatment arm.

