## **INCLUSION AND EXCLUSION CRITERIA**

### **Inclusion Criteria**

Subjects must meet ALL the following criteria to be eligible for study enrollment:

- $\geq 18$  years of age;
- Candidate for ureteroscopy with holmium laser lithotripsy;
- Total renal stone burden of 7 mm - 20 mm as measured by the sum of the longest dimension from the axial, coronal or sagittal view (whichever is longest) of each stone on CT within 90 days before the index procedure;
- At least one renal stone  $\geq 7$ mm as measured by the longest diameter from the axial, coronal or sagittal view (whichever is longest) on CT within 90 days before the index procedure;
- Be willing and able to return for and respond to all study-related follow up procedures; and,
- Have been informed of the nature of the study, agreeing to its requirements, and have signed the IRB approved ICF.

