**ENROLLMENT AND RANDOMIZATION**

Study subjects will be enrolled and randomized to treatment intraoperatively. If a subject requires treatment of ureteral calculi, treatment of the ureteral stones should be completed prior to randomization. If ureteral perforation(s) occur as a result of a stent or the treatment of ureteral calculi prior to randomization, the subject should not be enrolled or randomized.

Once all ureteral stones are treated, eligibility has been confirmed based on successful placement of the ureteral access sheath and visual inspection of the collecting system and kidney stones via retrograde pyelogram, the subject is ready for enrollment. At that time, subjects will be randomized intraoperatively with a 1:1 ratio of test-to-control subjects. The subject is considered enrolled into the study at the time of randomization just prior to commencement of lithotripsy of the renal stones.

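### The synopsis does not use baseline stone burden in the primary comparison; pre-specifying an adjusted risk difference would be a cheap gain in efficiency, not the repair of an error

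*Combined protocol and SAP*

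**What the plan says.** Four parts of the synopsis in the Combined protocol and SAP bear on this point.

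- **Primary Endpoint.** Stone free means no fragment of any size on the 30-day CT, read centrally and blind. "The SFR is calculated by determining the number of subjects in each treatment arm with a stone free status of" yes, and that number is divided by the number treated in the arm. No covariate is mentioned.
- **Sample Size.** With 25% stone free in both arms, N=116 ("58 per group using 1:1 randomization") "produces at least 80% power to reject the non-inferiority null hypothesis assuming a one-sided" 0.05 normal approximation test. The margin does not appear in this text.
- **Enrollment and Randomization.** "subjects will be randomized intraoperatively with a 1:1 ratio of test-to-control subjects". No stratification factor is named.
- **Inclusion Criteria.** "Total renal stone burden of 7 mm - 20 mm as measured by the sum of the longest dimension" of each stone, on a CT taken within 90 days before the procedure. Total burden is therefore known for every randomised subject before assignment.

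**The concern.** Total burden may vary almost three-fold between subjects (20/7 = 2.9) and plausibly predicts whether any fragment remains at 30 days. If it does, a comparison of crude proportions leaves explainable variation in the standard error, and a chance difference in burden between the arms passes straight into the estimated difference. With 58 per arm, power barely at 80% and no balancing factor named, a covariate that every site must measure anyway is worth using. What is at stake is a few points of power and how well the result stands up if the arms happen to differ in burden. The validity of the test is not at stake.

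**Working it through.** **Inputs from the documents.** One-sided alpha 0.05; 25% stone free in each arm; 58 per arm; 1:1 allocation; burden 7 to 20 mm.

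**Assumptions.** Margin (solved from N below); burden uniform on 7 to 20 mm, so SD = 13/√12 = 3.75 mm; odds ratio (OR) of not being stone free per SD of burden from 1.0 to 2.5. The documents give no figure for the last.

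**Step 1: reproduce the plan's figure.** The variance term is 2 × 0.25 × 0.75 = 0.375.

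- Implied margin = (1.645 + 0.842) × √(0.375/58) = 0.1999, so 20 points.
- n per arm = 0.375 × (1.645 + 0.842)² / 0.20² = 57.96, rounded up to 58.
- Power at 58 = Φ(0.20/√(0.375/58) − 1.645) = 80.02%. Exact enumeration gives 80.5%.
- Margins of 15 and 25 points would need 104 and 38 per arm, so 20 is the round value that fits. Because it was solved from N, this shows consistency and is not independent confirmation.
- At 57 per arm, power is 79.4%.

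**Step 2: what adjustment could add.** On the risk-difference scale, adjustment multiplies the variance by about (1 − R²), where R² = Var[p(burden)] / (0.25 × 0.75). Power = Φ(0.20/√(0.375(1 − R²)/58) − 1.645).

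| OR per SD | Stone free at 7 mm / 20 mm | R² | Adjusted power, formula | Simulated crude vs adjusted |
|---|---|---|---|---|
| 1.0 | 25% / 25% | 0 | 80.0% | 80.8% vs 80.0% |
| 1.5 | 39% / 14% | 0.029 | 81.1% | 80.2% vs 80.6% |
| 2.0 | 50% / 8% | 0.080 | 82.8% | 80.3% vs 82.4% |
| 2.5 | 57% / 5% | 0.128 | 84.6% | 80.1% vs 83.7% |

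The simulations compare the crude z-test with a logistic model (arm, burden) standardised to a risk difference with an influence-function standard error. A separate set of 8,000 trials per setting gave 80.6% vs 79.9%, 80.6% vs 81.1% and 80.1% vs 82.5% at ORs 1.0, 1.5 and 2.0. Monte Carlo error at that size is about √(0.8 × 0.2/8,000) = 0.4 points per figure.

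In subjects, OR 2.0 is worth 58/(1 − 0.080) − 58 = about 5 per arm, and OR 1.5 is worth 58/(1 − 0.029) − 58 = about 2 per arm.

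**Step 3: chance imbalance, OR 2.0.** The SE of the between-arm difference in mean burden is √(2/58) = 0.186 SD. An imbalance of 1.96 SE moves the crude difference by about 4.4 points.

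In the roughly 15% of simulated trials where the CVAC arm drew larger burdens by more than 1 SE, crude power was 67.5% and adjusted power 82.9%. A repeat with new random numbers gave 70.2% and 83.9%. In the mirror-image trials crude power rises, so the average in Step 2 is the long-run net effect.

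**Step 4: type I error at the margin.** Crude vs adjusted was 4.8% vs 4.9% (45% vs 25% stone free), and in two sets 6.2% vs 6.2% and 5.8% vs 5.9% (25% vs 5%). Adjustment does not loosen the test. It also does not remove the slight excess at low rates, which both methods share.

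**The case against.** The strongest reply is that nothing here is wrong. Under randomisation the crude risk difference is valid. The Sample Size section claims power for that test, and on the inferred margin the claim holds. Chance imbalance is already part of the crude test's variance and unconditional error rate, so it is not a bias. All of this stands.

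A reader might infer that the plan ignores stone burden. The documents do not support that. The quoted sentence defines the endpoint, and the test appears only as a sample-size assumption. The text available for this review ends within the synopsis and does not show even the margin, so the detailed analysis section may well name covariates or strata.

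A reader might also infer that the crude analysis certainly gives up a material amount of power. That depends on a prognostic strength the documents do not state, and eligibility narrows the range of burden. The range spans 13/3.75 = 3.46 SD, so OR 2.0 per SD already means an 11-fold odds gradient (2^3.46) between the smallest and largest burdens. OR 1.5 means about four-fold and yields only 0.5 to 1 point.

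Nor should adjustment be read as a cure for the thin power. At 40% stone free in both arms and OR 2.0, simulated power is 70.0% crude and 74.1% adjusted, still below 80%. Sensitivity to the assumed rate, and to loss of evaluable subjects, is a separate planning matter.

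What the reply does not remove is the balance of cost and benefit: the covariate is already collected, the loss is under 1 point at worst, and the protection is real if burden matters.

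**Conclusion.** The point holds as an optional but worthwhile efficiency improvement. Nothing in the synopsis uses baseline burden in the primary comparison, although eligibility guarantees that it is recorded before randomisation. At 25% in both arms the expected gain is about 0.5 to 1 point of power at OR 1.5 per SD, about 2 at 2.0 and about 4 at 2.5. Type I error is essentially the same, and less depends on the luck of the allocation.

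These figures rest on a 20-point margin solved from N, a uniform spread of burden and assumed odds ratios. The conclusion does not extend to saying that the planned test is invalid, that its stated power is not met, or that the full plan omits adjustment.

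**What to change.** First check the detailed analysis section. If it already adjusts for burden, a cross-reference from the synopsis is enough. If it does not, pre-specify before unblinding:

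- a logistic model with arm and baseline total stone burden in mm as a continuous term, stating which reading of the eligibility CT supplies the value;
- the primary estimate as the risk difference obtained by standardising that model over all analysed subjects, with an influence-function standard error;
- the same margin and the same one-sided 0.05. A conditional odds ratio should not replace the risk difference, because the margin would lose its meaning;
- the crude difference as a sensitivity analysis.

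The cost is SAP wording and a few lines of code, with no new data and no extra subjects. The downside is under 1 point of power if burden proves not to be prognostic.

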**OPERATIVE TREATMENT**

The site research clinical coordinator or other designated study personnel will be present in the surgical suite during each of the operative procedures to confirm final eligibility criteria, perform randomization and collect the operative data required for eDC entry detailed further in the sections that follow.

*Laser Lithotripsy:* Once a subject is randomized, the Investigator should adhere to the assigned method of stone removal. The goal of all index procedures is rigorous removal of stones and fragments to actively render the subject stone free. Basketing is allowed as an adjunct to SURE procedures in order to render the subject stone free. Ureteroscopic laser lithotripsy should be performed per physician preference given the assigned mechanism of removal, stone location and composition, and the best interest of the patient. The laser settings can therefore be adjusted as needed to accommodate the method of removal, stone location, and the stone composition. To provide homogeneity in lithotripsy methodology, 30 watt lasers are excluded from use in the study procedures.

*Stent Placement & Removal:* At the conclusion of the stone removal procedure, retrograde pyelogram will be performed prior to placement of the ureteral stent to assess any damage to the kidney or ureter. The post-operative stent will be placed and should remain for a minimum of three (3) days and removed thereafter at the Investigator's discretion. Subjects should be advised not to self-remove the stent; the stent should be removed in clinic at the post-op visit.

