**Table 1: ASPIRE Study Procedure Overview**

Test or Procedure	Screening/ Baseline (-30 days)	Operative/ Discharge (Day 0)	Post- Op	30 days (-10/+20 days)	3 months (± 14 days)	6 months (± 14 days)	12 months (± 45 days)	18 months (± 45 days)	24 months (± 60 days)	Unscheduled Visit
	Clinic	OR	Clinic	Phone + CT	Phone	Phone	Phone	Phone	Phone	Clinic or Phone
Informed consent	X									
Demographics	X									
Medical History	X									
Non-contrast CT 	X 			X						C
KUB x-ray or KUB US 	C									C
Physical Exam	X									
Labs 	X									C
UA, culture 	X									C
Pregnancy Test 	X									
Con. Medications	X	X	X	X	X	X	X	X	X	X
Randomization		X 								
Procedure Timing, Image/Video		X								C
Retrograde Pyelogram	X									
Investigator Survey	X									
UB-04 & EOB Capture 	X									X
Stent Removal 			X							
Patient Reported Outcomes	X			X	X	X	X	X	X	X
Adverse Events		X	X	X	X	X	X	X	X	X
Stone Events			X	X	X	X	X	X	X	X

KEY: "X" = required procedure; "C" = procedure not required, but images and/or results captured if performed

 If NCCT, KUB or KUB/US are performed per standard of care or out of clinical necessity at or in between any clinic visit, results will be captured as a part of study

 Captured ≤ 90 days prior to index treatment date; refer to image acquisition protocol for CT acquisition parameters

 Roll-in training subjects will not be randomized and automatically assigned to CVAC®

 To rule out active infection and within 30 days of index procedure

 Fertile women only and within 48 hours of index procedure

 UB-04 and EOB forms are captured for the index procedure and any visits or procedures administered for stone events, reinterventions, retreatments or unscheduled visits.

 Stents removed at three (3) or more days following the index procedure. Stents must be removed prior to 30 day CT.

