## STUDY DURATION

The anticipated study start date is May 2021 followed by approximately 18 months of enrollment. The study will last for 2 years following each subject's ureteroscopy index procedure, until the last subject completes 24-month telephone follow up or is withdrawn from the study. The anticipated study close-out date is January 2025.

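### Read literally, the synopsis stone-free formula counts a missing 30-day CT as not stone free; with a difference-scale margin and CT loss that is similar in both arms and unrelated to outcome, this raises the false non-inferiority rate

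*Combined protocol and SAP*

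**What the plan says.** All references are to the Combined protocol and SAP, Section 1.0 (Protocol Synopsis).

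- **Primary Endpoint.** Stone-free status requires "zero residual fragments at 30 days observed on non-contrast CT (NCCT) by blinded central reviewer(s". The rate is the count of stone-free subjects in an arm, obtained by "dividing that by the total number of subjects treated in the respective treatment arm". This text does not mention missing CTs.
- **Sample Size.** With 25% stone free in both arms, 116 subjects (58 per arm) "produces at least 80% power to reject the non-inferiority null hypothesis assuming a one-sided" 5% normal-approximation test. It does not say whether the 58 are treated subjects or subjects with an evaluable CT. Neither the margin nor its scale appears in the synopsis.
- **Study Duration.** Each subject is followed "until the last subject completes 24-month telephone follow up or is withdrawn from the study", so withdrawals are foreseen.
- **Table 1.** The CT belongs to the 30-day contact, with a window of -10/+20 days. Footnote 7 adds: "Stents must be removed prior to 30 day CT".
- **Provisions that limit CT loss.** Under Operative Treatment, "the stent should be removed in clinic at the post-op visit". Under Inclusion Criteria, a subject must "Be willing and able to return for and respond to all study-related follow up procedures".

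**The concern.** A positive status needs a CT that was read, but the denominator does not. A treated subject with no readable CT cannot enter the numerator and stays in the denominator, which amounts to scoring missing as failure.

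That rule is often called conservative. In a superiority test it usually is. In a non-inferiority test on a difference it need not be, because failures added at the same rate to both arms pull the two observed rates together while the margin stays where it was. Losing primary data would then make a truly inferior result easier to pass, and would raise apparent power when it ought to cost power. A few absent scans could decide the primary conclusion.

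**Working it through.** **Inputs from the synopsis:** 25% stone free in both arms, 58 per arm, one-sided 0.05, at least 80% power, normal approximation. **Assumptions:** the margin and the CT-loss rate, neither of which the synopsis gives.

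**1. Reproduce the sample size and infer the margin.** For a difference margin of 0.20:

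n = (1.645 + 0.842)² × 2 × 0.25 × 0.75 / 0.20² = 57.96, so 58 per arm and 116 in total.

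A margin of 0.19 gives 65 per arm and 0.21 gives 53. A 20-point difference margin with no allowance for CT loss therefore fits the stated figure closely, but it remains an inference.

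**2. Effect of the printed formula.** Let pB and pC be the true stone-free rates (basket, CVAC), and sB and sC the CT loss among truly stone-free subjects. The expected observed difference is

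pC(1 − sC) − pB(1 − sB) = (pC − pB) + (pB·sB − pC·sC).

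If both losses equal m, this is (pC − pB)(1 − m). At 10% loss a true 20-point deficit is observed as 20 × 0.9 = 18 points, against a margin still at 20. The bias is zero when no stone-free subject is lost. It reverses when sC/sB exceeds pB/pC, which is 5.0, 2.3, 1.8 and 1.5 in the four scenarios below.

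**3. False non-inferiority rate under the printed formula.** Exact binomial enumeration of the unpooled Wald test, 58 per arm, true rates at the null boundary, equal loss unrelated to outcome:

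| Basket vs CVAC | 0% | 1% | 3% | 5% | 10% | 20% |
|---|---|---|---|---|---|---|
| 25 vs 5 | 5.9% | 6.2% | 7.1% | 8.0% | 10.7% | 18.6% |
| 35 vs 15 | 5.3% | 5.6% | 6.2% | 6.9% | 8.9% | 14.6% |
| 45 vs 25 | 5.1% | 5.3% | 5.9% | 6.5% | 8.1% | 12.6% |
| 60 vs 40 | 4.3% | 4.5% | 5.0% | 5.5% | 6.9% | 11.0% |

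From unrounded rates, the rise over no loss is 0.2 to 0.4 points at 1%, 0.6 to 1.2 at 3% and 2.5 to 4.9 at 10%. In the 25 vs 5 row, 0.9 points of the excess over 5% is small-sample Wald error that is present without loss. A restricted-likelihood score test in that scenario still moves from 5.0% to 9.1% at 10% loss, so the rise does not come from the choice of test.

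**4. Dependence on the margin and its scale** (normal approximation, basket 25%, 10% loss, 58 per arm). Difference margins of 15 and 10 points give 7.8% and 6.6%, so the direction is unchanged. On a risk-ratio scale the factor (1 − m) cancels and the nominal error stays at 5.0%. On an odds-ratio scale it is 5.4%.

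**5. Candidate rules under three loss patterns.** Error in the order 25 vs 5, 35 vs 15, 45 vs 25, 60 vs 40:

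| Loss pattern | Printed formula | Evaluable CTs only | Both must reject |
|---|---|---|---|
| 10% random in each arm | 10.7/8.9/8.1/6.9% | 6.2/5.2/5.0/4.9% | 6.2/5.1/4.8/4.2% |
| CVAC loses 10%, residual-fragment subjects only; basket complete | 5.9/5.3/5.1/4.3% | 7.1/7.6/8.8/11.9% | 5.9/5.3/5.1/4.3% |
| CVAC loses 10%, residual-fragment subjects only; basket loses 10% at random | 12.1/12.3/13.4/14.7% | 7.2/7.6/8.9/11.7% | 7.2/7.5/8.5/10.2% |

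**6. Power at 25% in both arms.** With no loss it is 80.5%. At 10% random loss it is 83.1% under the printed formula, 76.7% with evaluable CTs only, and 76.4% when both must reject.

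**7. Illustration, deliberately near the boundary.** Take 58 treated and 52 CTs read per arm, with 13 basket and 9 CVAC subjects stone free.

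- Printed formula: 9/58 − 13/58 = −6.9 points, lower bound −18.8, passes.
- Evaluable CTs: 9/52 − 13/52 = −7.7 points, lower bound −20.8, fails.

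**The case against.** The strongest reply is about scope. Only the synopsis was available, and its endpoint sentence defines a rate in passing. The denominator may be shorthand for an analysis set defined in a later section. A reader might infer that the trial will score absent CTs as failures. The documents do not support that: they show only what the printed formula does if it is followed and nothing else governs. This part of the reply stands.

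It also stands that the inflation needs a difference-scale margin, which is inferred, and that no CT-loss rate is given. The withdrawal wording concerns the end of a 24-month follow-up and footnote 7 is a sequencing rule. They show that a treated subject can lack a CT, not that many will. In-clinic stent removal, the follow-up criterion and the wide CT window all work against loss, and at 1 to 3% loss the effect is small.

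A second tempting inference is that an evaluable-CT analysis should simply replace the printed one. The second row of the table in step 5 refutes it: when CVAC loses only residual-fragment subjects and basket CTs are complete, the printed formula holds its level and the evaluable-CT test does not. That objection is correct, and it is why the fix keeps both.

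The reply does not remove the core. The formula as printed does assign a status to a missing CT, and under plausible conditions the assignment favours a non-inferiority claim.

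**Conclusion.** The concern holds in a limited form, and the text should be fixed; confidence is medium. Three conditions together produce the inflation: a margin on the difference scale, CT loss that is similar between arms, and loss unrelated to stone-free status. The size is then set by the loss rate, which is unknown: negligible at 1%, and material at 10%, where the error reaches 6.9% to 10.7% depending on the true rates.

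It would be wrong to read this as saying that the printed formula always inflates error. There is no effect with complete CTs, with loss confined to residual-fragment subjects, or (nominally) with a risk-ratio margin. If no stone-free basket subject is lost but 10% of stone-free CVAC subjects are, the error falls to 5.1/3.5/2.7/1.5%.

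The Sample Size text has a related gap: if the inferred margin is right, 58 per arm leaves no room for missing CTs, and the synopsis does not say which count it refers to.

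**What to change.** **Primary Endpoint.** Keep the treated-subject analysis and add text along these lines: *The non-inferiority test is also performed in treated subjects with an evaluable 30-day NCCT. Non-inferiority is claimed only if both tests reject. Missing CTs and their reasons are reported by arm. A two-way tipping-point analysis varies the number stone free among subjects without an evaluable CT from none to all in each arm and reports where the conclusion changes.* Define evaluable, for example as read by the central reviewer and acquired within the Table 1 window. Make the synopsis agree with any missing-CT rule elsewhere in the protocol or SAP. Whether the population should be treated or randomized subjects is a separate question and is left alone here.

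The tipping-point analysis is needed because requiring both tests does not remove all inflation under arm-specific informative loss (third row of the table in step 5). In the illustration in step 7, with all missing CVAC subjects counted as failures, one stone-free subject among the six missing basket subjects moves the lower bound under the printed formula from −18.8 to −20.7 and reverses its conclusion.

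**Sample Size.** State the margin and its scale if they are not given elsewhere, say whether 58 per arm means treated subjects or evaluable CTs, and restate power with CT loss: about 78% at 5% and 76% at 10% random loss when both tests must reject, against 80.5% with none.

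**Cost.** A few sentences, a little more analysis and a less favourable power statement. No extra procedures are needed, and no extra subjects if the lower power is accepted. If it is not, about 65 per arm gives 80.6% power for the evaluable-CT test at 10% random loss.
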